----------------------------	---

Clinical Trial Protocol

Page 7 of 140

Proprietary confidential information © 2022 Boehringer Ingelheim International GmbH or one or more of its affiliated companies

	
IMV cohort, adjustment will be made for the baseline WHO value, baseline D-Dimer level and age.
 
For each of the two key secondary endpoints, treatment failure at Day 28 and all cause mortality at Day 28, the delta method and average marginal effect method will be used to calculate the risk difference, 95% confidence intervals and p-values. Adjustment will be made for the same set of covariates as in the primary analysis of the primary endpoint.
 
Descriptive statistics will be used to analyse all other endpoints and for all analyses of the IMV patient cohort.
 
If the NIV and IMV patient cohorts show homogeneity, then a meta-analysis will be performed to obtain an overall treatment estimate, albeit in an exploratory manner.

--	---

Clinical Trial Protocol

Page 8 of 140

Proprietary confidential information © 2022 Boehringer Ingelheim International GmbH or one or more of its affiliated companies

FLOW CHART

Trial Periods	Screening	Intravenous open-label treatment					Follow-Up			
Visit number	1	2a	2b	2c	2d	2e / EOT	3	4	5	6 / EOS
Day	0	1	2	3	4	5	6	7	28	90
Hours	-24 - 0	0-14	26-38	50-62	74-86	98-110	134			
Time windows [hrs, if not specified otherwise]		+6	±2	±2	±2	+6	±12	+1 day	+2 days	±7 days
Informed consent (separate IC for patients participating in PK sampling)	X									
Demographics	X									
Medical history	X									
Physical examination	X					X			X	
Weight	X									
Height	X									
Vital signs ¹	X	X	X	X	X	X	X	X	X	
12-lead ECG ²	X	(X only needed in case of clinical event) ²								X
Review of in-/exclusion criteria	X									
IRT call	X	X				X				
Randomisation ³		X								
Dispense trial drugs	X									
Administer trial drug ⁴		X	X	X	X	X				
PK Sampling ⁵		X								
Laboratory Tests ⁶	X			X		X	X ⁶		X	
D-dimer assessment ⁷	X			X		X		X	X	
Fibrinogen, aPTT and antithrombin assessment ⁸	X	X	X	X	X	X	X	X	X	
PaO ₂ /FiO ₂ ratio (or inferred PaO ₂ /FiO ₂ ratio from SpO ₂) ⁹	X	X	X	X	X	X	X	X	X	

Trial specific examinations: SOFA score ¹⁰	X						X		X	
11-point WHO Clinical Progression Scale (see Section 5.1.1) ¹¹	X	X	X	X	X	X	X	X	X	
Pregnancy testing ¹²	X								X	
SARS-CoV-2 test ¹³	X									
All adverse events/Serious adverse events ¹⁴	X	X	X	X	X	X	X	X	X	
Concomitant therapy	X	X	X	X	X	X	X	X	X	

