Similarly, in patients with acute MI where alteplase doses (up to 100 mg) given over 90 min were applied, the risk of intracranial haemorrhage is <1%. In multivariable models the main risk factors were older age, female sex, black ethnicity, systolic blood pressure (BP) of 140 mm Hg or above, diastolic blood pressure of 100 mm Hg or above, history of stroke, alteplase dose of more than 1.5 mg/kg, and lower body weight [[P98-10462](#)].

In the Phase II part of the current trial, no new safety signals were identified. Major bleeding events until Day 6 were overall infrequent (1 patient in the 0.3/0.02 mg/kg dosing group and 3 patients in the 0.6/0.04 mg/kg dosing group), and a trend towards a dose-dependent increase was mainly observed for non-major bleeding events.

Mitigation strategies to prevent bleeding events in Phase III (Part 2) of the current study are implemented in [Section 3.3.4.1](#).

Hypersensitivity

Further known risks of alteplase are hypersensitivity reactions. These can occur at any time and are not predictable. If detected at an early stage, any form of hypersensitivity reaction (anaphylaxis, anaphylactic reactions like angioedema) can be effectively treated with medication such as adrenaline/epinephrine, glucocorticoids, antihistamines, complement inhibitor, bradykinin antagonists and fluids.

Effect of Alteplase on D-Dimer and fibrinogen

In patients with acute myocardial infarction (AMI) or deep vein thrombosis (DVT), D-dimer and fibrin degradation products significantly increased during administration of alteplase, while fibrinogen and plasminogen concentrations significantly decreased compared to baseline [[P90-52475](#), [P91-62566](#)]. The increase in D-dimer levels was correlated with thrombus mass and can be considered as indicator for efficient thrombolytic treatment in AMI and DVT patients [[P90-52475](#), [P92-71704](#)].

Overview of trial-related risks

An overview of trial-related risks is provided in [Table 1.4.2:1](#).

Clinical Trial Protocol

Page 28 of 140

Proprietary confidential information © 2022 Boehringer Ingelheim International GmbH or one or more of its affiliated companies

Table 1.4.2:1 Overview of trial-related risks

Possible or known risks of clinical relevance for this trial	Summary of data, rationale for the risk	Mitigation strategy
Investigational Medicinal Product / alteplase		

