Cardiovascular: hypotension, bradycardia GI: nausea, vomiting, GI tract bleeding Haematologic: spontaneous bleeding, bone marrow depression Musculoskeletal: musculoskeletal pain Respiratory: Pulmonary edema Skin: bruising, flushing Other: fever, edema, phlebitis	More detailed description see IB, Section 7.6	Timely detection, evaluation, and follow-up of laboratory alterations in selected laboratory parameters to ensure patients' safety. ECG monitoring in ICU, repeated ECGs. Monitoring for bleeding including neurological assessment to rule out intracranial haemorrhage. Monitor hypersensitivity reactions such as angioedema, profound hypotension, rash, urticaria. Supportive treatment for bleeding including infusion therapy, red blood cell (RBC) and FFP transfusion. In case of hypersensitivity glucocorticoids, antihistamines, and adrenaline (epinephrine) address acute hypersensitivity. Intubation readiness

Clinical Trial Protocol

Page 29 of 140

Proprietary confidential information © 2022 Boehringer Ingelheim International GmbH or one or more of its affiliated companies

Table 1.4.2:1

Overview of trial-related risks (cont)

Clinical events		
Minor bleeding particularly traumatic –at site of venepuncture		Supportive treatment, and use caution during suction, measurement of plasma fibrinogen levels
Major bleeding including intracerebral haemorrhage or bleeding from a critical organ	Common	Measurement of plasma fibrinogen levels, recommendation to stop alteplase infusion, and administer fibrinogen concentrate or cryoprecipitate, if fibrinogen is <150 mg/dL and other supportive treatment including i.v. tranexamic acid should be considered
Hypersensitivity reactions (e.g. rash, urticaria, bronchospasm, angio-oedema, hypotension, shock).	Rare	Anti-allergic medications
Serious anaphylaxis	Very rare	Treat per local protocols and stop further administration of medication
Other risks		
Additional blood samples	Bleeding related to venipuncture	Compression
Transfusion of blood products, fibrinogen or supportive treatment like i.v. tranexamic acid.	Related to bleeding event. Anaphylaxis due to transfusion.	Treatment as per local protocols and product information

Risk evaluation in relation to COVID-19:

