1.4.3 Discussion

Consideration of therapies that are not recognized for this indication but of potential benefit, such as fibrinolytic agents, is warranted in this unprecedented public health emergency of COVID-19.

The bleeding risk described in the literature typically include high dosages of alteplase (up to 90 to 100 mg given as infusion over 1-3 hours) and the concurrent use of therapeutic antithrombotics. However, the alteplase short-term infusion dosages being used in this study (0.3 mg/kg/2h or 0.6 mg/kg/2h) are lower than those used in studies for MI, massive PE and stroke. Additionally, by the low dose during long-term infusion over 12 hours, the rapid inactivation of alteplase in the circulation is projected to be associated with plasma fibrinogen levels well above the threshold of 150 mg/dL, which are known to be linked to the risk of bleeding [[c32479735-01; P13-13102](#)]. The safety results from Phase II (part 1) of the current trial were generally comparable across the treatment groups, except for bleeding events, which are a known side effect of alteplase. In Phase II, mainly non-major bleeding events were observed, and some of them were related to interventions. Additional risk minimization strategies to avoid intervention-related bleeding events have accordingly been implemented for Part 2, phase III of the study.

The bleeding risk is predicted from the plasma fibrinogen level which provides a measure of the alteplase absorbed. This will be monitored and if the level falls below 150 mg/dL, alteplase has to be temporarily interrupted. Beside the extent of fibrinogen breakdown, D-Dimer levels, thrombocytopenia, the prolongation of the activated partial thromboplastin time (aPTT) will be monitored continuously. Furthermore, elevated blood pressure as a risk of intracranial hemorrhage and the co-administration of ACE inhibitors related to the risk of angioedema will be monitored.

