25. Ischaemic stroke or transient ischaemic attack (TIA) in the preceding 6 months
26. Patients who must or wish to continue the intake of restricted medications (see [Section 4.2.2.1](#)) or any drug considered likely to interfere with the safe conduct of the trial. Re-screening is allowed once within the same hospital stay.
27. Women who are pregnant. (Note that women of childbearing potential are not excluded as eligible patients are severely ill during the observation period of the trial.)
28. End stage renal disease (Stage ≥ 4) or need for renal replacement therapy at baseline
29. Need for ECMO at baseline
30. Platelet count $<100 \times 10^9/L$ or history of Heparin-Induced Thrombocytopenia
31. Lumbar puncture within past 3 days
32. Known abdominal or thoracic aneurysm
33. Active tuberculosis

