The interruption intervals for concomitant heparin treatment before an intervention should follow local practice. Please see product information of respective heparins for appropriate interruption intervals before intervention (for temporary interruption of alteplase, please see [Section 3.3.4.1](#)).

The anti Xa level should be monitored regularly, in patients with mild to moderate renal impairment. The aPTT level should be monitored at least daily and preferably more frequently, while given concomitantly with alteplase.

Occurrence of heparin-induced thrombocytopenia (HIT) must result in cessation of UFH or LMWH without recommencement regardless of treatment assignment. Use of an acceptable alternative agent is required in this instance as clinically indicated. Occurrence of HIT has to be reported as adverse event (AE).

Glucocorticoid treatment

Current or scheduled use of systemic (intravenous or oral) corticosteroid therapy should be included in the SOC regimen (e.g. 6 mg of dexamethasone orally) for up to 10 days or until hospital discharge. As patients in the alteplase treatment arm should also receive best possible SOC, this recommendation applies in the vs. non-invasive alteplase arm as well.

Total daily dose equivalencies to dexamethasone 6 mg are provided in [Appendix 10.6](#).

Standard of Care (SOC) arm

SOC includes any supportive measures applied in hospital, specifically on an ICU, such as for example the use of non-invasive or invasive ventilation, oxygen masks, haemodynamic support, if needed, sedation, as well as medical therapies commonly used in patients suffering from ARDS or its complications. SOC should include best possible treatment regimen established locally and should be in line with current guidelines for COVID-19 ARDS treatment.

For additional recommended SOC therapies please refer to [Appendix 10.6](#).

Recommendations before the start of alteplase:

- Arterial lines and central venous catheters, tubes (e.g. for intubation and feeding) and drains (e.g. pleural and abdominal) should be placed at least 6 hours before starting the first treatment with alteplase.
- A delay of the alteplase treatment of approximately 6 hours after the insertion of the last line/catheter is recommended to allow for complete hemostasis (this time-period can be extended to up to 24 hours after complicated interventions)

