- Before the start of the very first alteplase infusion, there should have been a time period of at least 10 hours since the last LMWH (S.C.) administration to ensure no significant overlap of the LMWH and alteplase.

Emergency procedures

Management of Bleeding during Alteplase Treatment:

- In case of bleeding, the alteplase infusion can be interrupted up to a maximum of 72 hours.
- A restart is possible, if complete haemostasis is achieved, and if lab results support a restart (fibrinogen $\geq 150\text{mg/dL}$, haemoglobin is stable, anti-Xa 4 hours after s.c. administration is < 0.5 , or aPTT ratio is < 1.5 -fold of upper limit of normal).
- In case of interruptions of more than 12 hours, the time-windows for subsequent long-term infusions move accordingly, and the last long-term infusion may be given later than day 5 in the study. In total, up to 5x long-term infusions (of 12 hours each) can be given.

Management of serious bleeding events:

In case of serious bleeding, in particular cerebral or pulmonary haemorrhage, the fibrinolytic therapy must be discontinued, and concomitant heparin administration should be terminated immediately. Administration of protamine should be considered if unfractionated heparin has been administered. In patients who fail to respond to these conservative measures, judicious use of transfusion products may be indicated. Transfusion of cryoprecipitate, fresh frozen plasma, and platelets should be considered with clinical and laboratory reassessment after each administration. A target fibrinogen level of 1g/L (100 mg/dL) is desirable with cryoprecipitate infusion. Antifibrinolytic agents should also be considered.

Beyond patient-specific risk factors for bleeding, the bleeding risk can be estimated by the plasma fibrinogen level. Fibrinogen will be monitored daily during the treatment period with alteplase, and if the level falls below 150 mg/dL , the investigator should interrupt the alteplase infusion.

The alteplase infusion can be restarted, if fibrinogen recovers to $\geq 150\text{ mg/dL}$ during the following 72 hours.

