5.2.5.1 Bleeding events

Patients should be carefully assessed for signs and symptoms of bleeding. Bleeding definitions are provided below. The location of the bleeding including the specific critical area or organ into which the bleeding occurred (e.g. GI, intracranial, pulmonary bleed) and whether or not it prolongs hospitalization will be recorded.

Definition of any bleed

This is the sum of all major and minor bleeds.

Definition of a major bleed

Major bleeds will be defined according to the ISTH definition of a major bleed, as follows ([R05-0344](#)):

- Symptomatic bleeding in a critical area or organ, such as intracranial, intraspinal, intraocular, retroperitoneal, intra-articular or pericardial, or intramuscular with compartment syndrome,

and/or

- Bleeding associated with a reduction in hemoglobin of at least 2g/dL (1.24 mmol/L), or leading to transfusion of two or more units of blood or packed cells¹

and/or

- Fatal bleed

¹Bleeding should be overt and the hemoglobin drop should be considered to be due to and temporally related to the bleeding event.

Definition of a fatal bleed

Fatal bleeding is defined as a bleeding event that the investigator determines is the primary cause of death or contributes directly to death.

Definition of intracranial hemorrhage

Intracranial hemorrhage comprises the subtypes of intracerebral bleeds, subdural bleeds, epidural bleeds and subarachnoid bleed and will be recorded in eCRF.

Definition of a minor bleed

Minor bleeds are clinical bleeds that do not fulfill the criteria for major bleeds.

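### Section 1.4.3 promises ongoing watch on thrombocytopenia during alteplase plus heparin, but platelets are scheduled on only two of the five infusion days (minor)

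*Protocol*

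**What the plan says.** Section 1.4.3 of the protocol explains how bleeding risk will be controlled. After fibrinogen, it states that "D-Dimer levels, thrombocytopenia, the prolongation of the activated partial thromboplastin time (aPTT) will be monitored continuously".

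The timing is set elsewhere. The platelet count is a haematology item in Table 5.2.3:1, and Section 5.2.3 sends the reader to the flow chart for sampling days. There the laboratory-tests row is marked on Days 0, 3, 5, 6 and 28. Footnote 6 limits Day 6 to samples needed for SOFA and PaO₂/FiO₂; SOFA includes platelets (Appendix 10.1). The row "Fibrinogen, aPTT and antithrombin assessment" is marked on every day from 0 to 7 and on Day 28. Footnote 8 asks for fibrinogen daily and aPTT at least daily during treatment. Footnote 7 places D-dimer on Day 0 (or up to four calendar days before screening) and Days 3, 5, 7 and 28.

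The protocol acts on platelets in two main places. Exclusion criterion 30 in Section 3.3.3 bars patients with a count below 100 × 10⁹/L "or history of Heparin-Induced Thrombocytopenia". Section 4.2.1 says: "Occurrence of heparin-induced thrombocytopenia (HIT) must result in cessation of UFH or LMWH without recommencement regardless of treatment assignment".

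**The concern.** The Section 1.4.3 sentence is part of the case that the bleeding risk is acceptable, so it should match what sites are told to do. It makes the same statement about aPTT and about thrombocytopenia, yet aPTT is scheduled on all five infusion days and platelets on two. On those days alteplase is given together with prophylactic heparin, and Section 1.1 reports that in Part 1 major bleeds up to Day 6 occurred only in the alteplase groups. A falling count can be acted on only once it is measured, and the protocol does not require a measurement on Days 1, 2 or 4.

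What is at stake is the timeliness of one safety measurement. No efficacy comparison or trial conclusion depends on it.

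**Working it through.** The plan gives no figure to reproduce, so the check reads the flow-chart rows against the day header and then expresses the gap in infusion hours and calendar days.

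**Scheduled sampling on the infusion days (Days 1 to 5)**

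| Item | Days marked | Count |
|---|---|---|
| Fibrinogen | 1, 2, 3, 4, 5 | 5 of 5 |
| aPTT | 1, 2, 3, 4, 5 | 5 of 5 |
| Platelets (laboratory-tests row) | 3, 5 | 2 of 5 |
| D-dimer | 3, 5 | 2 of 5 |

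Sections 4.2.1, 5.2.3 and 6.2.2 and the SAP add no further platelet count in this period.

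**Infusion hours before the first scheduled post-dose count** (durations from Table 4.1.1:1; no interruptions and no optional second 2-hour infusion)

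- Day 1: 2 + 12 = 14 h. Days 2 to 5: 12 h each. Total: 14 + 4 × 12 = 62 h.
- Day 3 blood drawn before that day's infusion: 14 + 12 = 26 h; 26/62 = 41.9%.
- Day 3 blood drawn after it: 26 + 12 = 38 h; 38/62 = 61.3%.

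The documents do not say which of the two applies, so the result is a range of 42% to 61%.

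**The same with a count added on Day 2**

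- Before the Day 2 infusion: 14 h; 14/62 = 22.6%.
- After it: 14 + 12 = 26 h; 26/62 = 41.9%.

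**Calendar gap from the screening count to the first post-dose count**

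Section 4.1.3 allows randomisation on the day of screening or the day after.

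- Screening the day before: Day 0 to Day 3 = 3 days now; Day 0 to Day 2 = 2 days with the added count.
- Screening on the same day: Day 1 to Day 3 = 2 days now; Day 1 to Day 2 = 1 day with the added count.

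Three days is therefore an upper bound, and the added count shortens the first gap by one day in either case.

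**Volume of the added tests:** 2 counts × about 260 Part 2 patients = about 520 results at most, because discharge, death or withdrawal before Day 4 lowers the number.

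**The case against.** The strongest reply is that *continuously* is used loosely. Section 3.2 describes the DMC's safety role with the same word while having it review data at regular intervals, and aPTT in the quoted sentence is itself only daily. Section 1.4.3 is a discussion; the flow chart governs, so no site receives conflicting instructions. This stands, and it makes the wording part editorial. It does not explain why two quantities named together are scheduled at such different densities.

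Existing safeguards also count. Low platelets and previous HIT are excluded at entry. After a bleed, "A restart is possible, if complete haemostasis is achieved, and if lab results support a restart", and those results include stable haemoglobin, which belongs to the same panel as platelets, so a bleed is likely to prompt a count. Patients are closely watched and local teams may count platelets daily. Part 1 raised no new safety signal, and the documents give no thrombocytopenia or HIT rate that would show a need for more counts. All this limits the size of the point. Local practice is still not a protocol requirement, and Part 2 plans about 110 to 130 sites in about 22 countries.

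A reader might infer three stronger points that the documents do not support.

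- *That a stopping rule is undermined.* The restart rule in Section 4.2.1 names haemostasis, fibrinogen, haemoglobin and anti-Xa or aPTT. Platelets are not part of it.
- *That the extra counts would secure detection of HIT.* Heparin continues after the infusion days under local practice. Detection then rests on the later scheduled counts and local care, which counts on Days 2 and 4 leave unchanged.
- *That the neurological mitigation is contradicted.* Table 1.4.2:1 lists "Monitoring for bleeding including neurological assessment to rule out intracranial haemorrhage" without a tool or frequency, so no schedule conflicts with it. Section 5.2.5.1 adds that "Patients should be carefully assessed for signs and symptoms of bleeding". A daily coma score would not rule out intracranial haemorrhage and would tell little in sedated patients, so it is not proposed.

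**Conclusion.** The point holds as a minor mismatch in the safety schedule. Platelets are counted on two of five infusion days against five of five for fibrinogen and aPTT, and the first scheduled post-dose count comes after 26 to 38 of 62 planned infusion hours. These hours assume an uninterrupted course without the optional infusion; the range reflects the unstated draw time on Day 3. The Investigator's Brochure, to which Table 1.4.2:1 refers for more detail, is not available here, so wider monitoring advice there cannot be excluded.

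The added counts are worth making because they cost little and cover the days on which alteplase and heparin are combined. The documents do not show that the present schedule has caused or would cause harm.

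D-dimer is a different matter. Section 1.4.2 reports that in other indications "D-dimer and fibrin degradation products significantly increased during administration of alteplase", and no on-treatment rule uses it. More D-dimer sampling is not needed, only accurate wording.

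**What to change.** 1. In the flow chart, add a platelet count at the existing fibrinogen draw on Days 2 and 4. With the scheduled counts on Days 3, 5 and 6, platelets are then counted daily from Day 2 to Day 6. Day 1 is largely covered by the screening panel taken within the preceding 24 hours.
2. Do this in both arms, so that ascertainment of low counts stays comparable between them.
3. In Section 1.4.3, state the actual sampling: aPTT at least daily, platelets daily from Day 2 to Day 6, and D-dimer on Day 0 (or up to four calendar days before screening) and Days 3, 5, 7 and 28. The D-dimer change is editorial only.

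The amendment should not claim that these counts deal with HIT arising after the infusion days.

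The cost is a flow-chart and wording amendment and at most about 520 additional local platelet results to enter, with no new visit and no new blood draw. The laboratory tables in Section 7.8.2 of the Part 2 SAP are descriptive and arranged by day, so they would gain two days and need no new method.
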